## FAME-103B

### PROTOCOL SUMMARY

**Short Title:** FAME-103B

**Chairs :** [name]; [name] MPH

**Sample Size:** 30 pre-menopausal women without urogenital complaints

**Study Population:** The recruitment strategy is likely to capture a diverse population as this community is comprised of approximately 48% White, 48% African-American and 4% other ethnicities including Hispanic, Asian, Indian and Native American. Persons below the age of 18 will not be recruited.

**Study Sites:** UPMC Magee-Womens Hospital, Pittsburgh, PA

**Study Design:** Randomized cross-over study of self-insertion of two formulations of a placebo vaginal film

**Study Duration:** One study visit lasting approximately 90 minutes

**Study Film Products:** Two formulations of a placebo vaginal film (high and low level ammonio-methacrylate copolymer type B (Eudragit®))

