### **2.4 FAME-103B Rationale**

The objective of the FAME-103B study is to evaluate whether study participants can self-insert the high and low Eudragit® content placebo films. In previous vaginal film trials conducted at the University of Pittsburgh, participants have had variable success with self-insertion. As the Eudragit® film formulation as an extended platform moves forward with other active pharmaceutical ingredients in clinical trials, understanding whether the level of Eudragit® in the film impacts ease of insertion is vitally important.

In order to evaluate whether Eudragit® content impacts ease of self-insertion, participants will be asked to self-insert each placebo film and complete a survey reporting their perceptions and experience. Within 10 minutes of the insertion, clinical staff will perform a speculum exam to assess the location of the film and remove the residual film. This study poses minimal risks to participants as the safety of the high Eudragit® placebo film has already been evaluated in FAME-101 and found to be safe. The risk to study participants will also be minimized because the film will be removed immediately after insertion thereby limiting exposure to under 10 minutes for each film. The feasibility of easy film removal after self-insertion has been established by the clinical staff at the Reproductive Infectious Disease Unit at Magee-Womens Hospital who have removed film within 15 minutes of insertion in at least 40 prior participants. Thus, no technical or safety issues with film removal are anticipated.

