#### Clinical Safety Data

FAME-101 was a safety and acceptability study of the higher Eudragit® level. Sixty-four HIV uninfected, healthy women were enrolled. At enrollment the participants were randomized to timing of the follow-up visit. They then attempted self-insertion of the film. Immediately after this attempt, a clinician performed a visual inspection. If most of the film was visualized outside of the introitus, the film was removed by the clinician and a second film placed by the clinician during a speculum examination. Participants returned either 3,7,10 or 14 days after film placement depending on their randomization and then all participants returned for a final safety assessment three weeks after enrollment. Safety assessments, acceptability parameters, and changes to the vaginal microenvironment were assessed at each visit. The persistence of the film was noted.

Eighty-four participants were screened and 64 enrolled. The median age was 26.5 years; 56% were white and 27% non-Hispanic black. The primary endpoint was Grade 2 or higher AEs. There were 6 Grade 2 events; these included bacterial vaginosis, vaginal itching, pelvic cramping (2), friable cervix and adnexal pain. Of these, only bacterial vaginosis and vaginal itching were attributed to study product use. Forty-seven AEs were reported amongst 64 participants. Thirty-one participants (48.5%) reported at least one AE; 22 reported at least one urogenital event. For the women randomized to the 3 and 7 day follow up visit approximately 50% of the participants had visible film on speculum exam (44% and 56%). In summary, the high Eudragit® film was very well tolerated with no concerning safety signals.

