### 4.2 Recruitment

For this study, 30 pre-menopausal women, 18 – 45 years of age, will be enrolled over approximately a 3-month period. Participants may be recruited from medical clinics, local colleges, a list of previous study participants and the community by members of the Reproductive Infectious Disease Research staff. This recruitment strategy is likely to capture a diverse population as this community is comprised of approximately 48% White, 48% African-American and 4% other ethnicities including Hispanic, Asian, Indian and Native American. An IRB approved screening script may be used to provide study information and assess minimum eligibility during the recruitment process. After the study has been presented and questions have been answered, participants will be scheduled for an enrollment visit at UPMC Magee-Womens Hospital.

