## 6 Study Product

### 6.1 Regimen

Each participant will receive one vaginal film containing high level Eudragit® and one vaginal film containing low level Eudragit®.

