## **9 Statistical Considerations**

### **9.1 Sample Size and Accrual**

The primary aim of the study is to assess proper placement of two vaginal placebo films containing two levels of polymer. Secondary aims are to gather women's preference and experiences through questionnaire and discussion.

In a previous cross-over study of placebo film products, the proportion of 32 women that misplaced a 2" x 2" cellulose film was 41% and 78% misplaced a 1" x 2" film product, with 50% placement concordance between the two films. Twenty-five women will have 80% power to determine whether there is a difference between polymer types of vaginal placebo films based on a McNemar's test evaluated at the .05 significance level. The sample size of 30 women will allow for additional input regarding challenges.

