## **9.2 Statistical analyses**

McNemar's test will be used to assess differences in the proportion of misplaced films, defined as partial or unable to insert the vaginal film product based on visual assessment. McNemar's test will also be used to assess differences in preference for the two film products. Conditional logistic regression will be used to assess whether demographic characteristics such as age, race, and BMI are associated with product placement or product preference. Descriptive statistics will be used to summarize participants' challenges with self-insertion of the film products.

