## **9.4 Random assignment**

The randomization scheme will be generated and maintained by a member of the Data Management Center at the study site and supplied to the Pharmacy. Women will be randomized to the sequence of insertion of the two films, low followed by high Eudragit® content or high followed by low Eudragit® content in a 1:1 ratio using a permuted block design with random block sizes of 2 and 4. In order to minimize bias in group assignment, participants will be given study identification numbers. A study staff member will allot the identification numbers in sequential order as participants become eligible to enroll in the study. Participants will be randomized using REDCap's randomization module to obtain the sequence of product insertion. The film product will be labeled in order to mask the Eudragit® content to the participants and study staff. The randomization scheme will be created for a total of 34 participants; the overage will be created to compensate for participant withdrawals or unusable products.

---

 UNAIDS Women and Girls and HIV. Accessed at

[https://www.unaids.org/sites/default/files/media\\_asset/women\\_girls\\_hiv\\_en.pdf](https://www.unaids.org/sites/default/files/media_asset/women_girls_hiv_en.pdf)

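### Section 9.2: conditional logistic regression matched on the woman cannot estimate whether age, race or BMI is associated with placement overall, and the film-by-covariate terms it can estimate are not named

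*Combined protocol and SAP*

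**What the plan says.** Section 9.2 gives the covariate analysis one sentence: "Conditional logistic regression will be used to assess whether demographic characteristics such as age, race, and BMI are associated with product placement or product preference". It states no stratum and no model terms. It does not say whether association with placement means misplacing films in general or a difference between the two films. The sentence follows two McNemar tests, one of misplacement (partial or failed insertion) and one of preference. No other section supplies a model for these covariates.

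The design facts that matter are these:

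- Section 6.1: "Each participant will receive one vaginal film containing high level Eudragit® and one vaginal film containing low level Eudragit".
- Protocol Summary, study duration: "One study visit lasting approximately 90 minutes". Section 5.2 has height and weight taken at that visit.
- Section 9.4: "Women will be randomized to the sequence of insertion of the two films". Section 6.2 has the order of use documented.
- Section 2.4, on purpose: "understanding whether the level of Eudragit® in the film impacts ease of insertion is vitally important".

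Sections 3.1 to 3.4 list no objective or endpoint that concerns age, race or BMI.

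**The concern.** Conditional logistic regression compares records within a matched set. In this cross-over the only matched set is the woman with her two films. A characteristic that is the same for both of her films gives no contrast within the set, so the method cannot say whether older women, or women with a higher BMI, misplace films more often.

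The sentence can be read in two ways:

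- **Overall placement:** who misplaces films? The named method cannot answer this.
- **Differential placement:** does the difference between films vary with the covariate? The method can answer this, but only through film-by-covariate terms that Section 9.2 does not mention. A characteristic that affects both films alike would stay invisible.

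An analyst following the text would either report a coefficient with no meaning or choose another model after seeing the data.

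**Working it through.** **1. The plan's own figure.** Section 9.1 cites misplacement of 41% and 78% in an earlier study of 32 women, "with 50% placement concordance between the two films", and claims 80% power with 25 women. Take discordance pd = 0.50, difference d = 0.78 − 0.41 = 0.37 and two-sided 0.05 (sidedness is not stated):

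n = [1.96·√0.50 + 0.842·√(0.50 − 0.37²)]² / 0.37² = 26.2.

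Enumerating the uncorrected McNemar test at 25 women gives 80.2% power. The plan's figure reproduces, and nothing below changes it.

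**2. Why the main effects cancel.** For woman *i* with covariate x_i, let the log odds of misplacement be a_i + g·x_i for the low film and a_i + b + g·x_i for the high film. Women with two like placements contribute nothing to the conditional likelihood. For a woman with exactly one misplaced film:

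P(high misplaced | one misplaced) = expit[(a_i + b + g·x_i) − (a_i + g·x_i)] = expit(b).

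The coefficient g has gone. With a film-by-covariate term h the probability becomes expit(b + h·x_i), so h can be estimated.

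**3. Numerical check.** Two simulated data sets of 30 women were used.

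- *14 discordant women.* The conditional log-likelihood was −7.6371 at age coefficients of −3, −1, 0, 1 and 3. With film-by-age instead, it was −7.7595, −7.6371 and −10.2332 at −1, 0 and 1.
- *16 discordant women, true age effect 0.6 per 5 years.* The log-likelihood was flat at −6.0122. Software returned an age coefficient of 0 with a standard error of about 1846. Film-by-age was estimable (1.72, SE 2.18). A GEE logistic model on the same data estimated the overall age effect as 0.49 (SE 0.20).

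**4. Women who inform film-by-covariate terms.** 30 × (1 − concordance) gives:

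- 50%: 30 × 0.50 = 15 (95% range 10 to 20)
- 70%: 30 × 0.30 = 9
- 90%: 30 × 0.10 = 3

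The 50% comes from a different film comparison; 70% and 90% are assumed. At the Section 9.1 values the discordant women split (0.50 + 0.37)/2 = 0.435 and (0.50 − 0.37)/2 = 0.065, or about 13 and 2 of 30.

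**5. Preference.** There is one choice per woman. On simulated choices, conditional logistic regression with a film-by-age term and ordinary logistic regression of the preferred film on age gave the same result (3.83, SE 1.60).

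**6. What a model for overall placement could detect.** GEE with exchangeable correlation, bias-reduced variance and t on 26 df; terms film, insertion order and one continuous covariate; 30 women randomised 15:15; 2,000 to 4,000 trials per cell. Effect sizes are assumed. The table shows the share of trials with the association detected.

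| Log odds ratio per SD | Misplacement 78% and 41%, concordance about 50% | 41% for both films, concordance 70% | 41% for both films, concordance 90% |
|---|---|---|---|
| 0.5 | 24–28% | 23% | 17% |
| 0.75 | 51–52% | 48% | 32% |
| 1.0 | 74–76% | 70% | 49% |
| 1.1 | 79% | not run | not run |

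For a two-group covariate the group share was set at 48% (Section 4.2, "approximately 48% White, 48% African-American and 4% other ethnicities") or 56% (Section 2.5, where in FAME-101 "56% were white and 27% non-Hispanic black"). Detection at an odds ratio of 3, 5 and 8 was 32.2%, 60.9% and 80.7% for the 48% share, and 33.3%, 61.5% and 80.3% for the 56% share. The GEE false-positive rate was 2.5–3.6%.

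For preference, logistic regression with one record per woman detected 0.5 per SD in 24–26% of trials and 1.0 in 63–70%. That likelihood-ratio test had a false-positive rate of 6%, so its figures are not strictly comparable with the GEE figures.

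**The case against.** The best defence is that the plan means differential placement. Conditional logistic regression is the regression extension of McNemar's test, the sentence follows two McNemar tests of film differences, and Section 2.4 asks about the effect of Eudragit level. On that reading the method is right and only the terms are missing. This reading is reasonable, but Section 9.2 does not state it, its words fit the overall question at least as well, and the terms would still have to be written down.

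It can also be said that the stratum is not given. That is true, but the woman is the only matching the design creates, and the McNemar tests in the same section already use it.

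The consequence is small: no listed objective depends on this analysis, and a standard error near 1846 would alert any analyst. That stands, and it limits the severity.

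Two cautions about the remedy also stand. The detection rates describe the replacement under assumed effects; they do not measure the defect. GEE and a random-intercept model estimate different odds ratios (population-averaged and woman-specific), and only GEE was simulated.

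**Conclusion.** The concern holds, as a minor point. With the woman as the matched set, information on the main effects of age, race and BMI is zero at any sample size; this is algebra and rests on no assumed rates. The estimable film-by-covariate terms are unnamed and would rest on about half of the women at the concordance cited in Section 9.1, and on fewer if the two films behave more alike. The preference analysis needs clarifying, not correcting. The primary comparison and the sample size stand. A suitable model for overall placement would still be limited with 30 women: under the most favourable margins simulated, about 80% detection needs a log odds ratio of 1.1 per SD, an odds ratio of about exp(1.1) = 3.0.

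**What to change.** Rewrite the covariate sentence in Section 9.2 to cover four things:

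1. **Placement question.** State whether overall or differential placement is meant, or both.
2. **Overall placement.** Name a logistic model on both films per woman with film, insertion order and one covariate at a time, clustered on woman. Use either GEE with a small-sample variance correction or a random intercept. Choose one in advance and say which odds ratio it estimates.
3. **Differential placement.** Keep conditional logistic regression only here, with the film-by-covariate terms named and the number of discordant women in each direction reported.
4. **Preference.** Name logistic regression of the preferred film on the covariate, one record per woman.

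Label all of these exploratory and state that 30 women can show only large associations. The cost is one paragraph of analysis wording. No new data, participants or procedures are needed, since insertion order is already documented under Section 6.2.

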## **9.4 Random assignment**

The randomization scheme will be generated and maintained by a member of the Data Management Center at the study site and supplied to the Pharmacy. Women will be randomized to the sequence of insertion of the two films, low followed by high Eudragit® content or high followed by low Eudragit® content in a 1:1 ratio using a permuted block design with random block sizes of 2 and 4. In order to minimize bias in group assignment, participants will be given study identification numbers. A study staff member will allot the identification numbers in sequential order as participants become eligible to enroll in the study. Participants will be randomized using REDCap's randomization module to obtain the sequence of product insertion. The film product will be labeled in order to mask the Eudragit® content to the participants and study staff. The randomization scheme will be created for a total of 34 participants; the overage will be created to compensate for participant withdrawals or unusable products.

---

 UNAIDS Women and Girls and HIV. Accessed at

[https://www.unaids.org/sites/default/files/media\\_asset/women\\_girls\\_hiv\\_en.pdf](https://www.unaids.org/sites/default/files/media_asset/women_girls_hiv_en.pdf)

